Subjects will be admitted to the clinical research unit (CRU) on Day -1. All doses will be administered in the morning of Day 1 as two 1-mL subcutaneous injections of 120 mg/mL solution of LY2951742. Subjects will be stratified to receive injections in the upper arm, abdomen, or thigh. Subjects will remain resident at the CRU until the procedures scheduled at 24 hours postdose have been completed on Day 2, or longer at the discretion of the investigator. All subsequent procedures will be performed on an outpatient basis.

Blood samples will be collected up to 20 weeks postdose to determine serum concentrations of LY2951742 for PK assessments and plasma concentrations of CGRP for PD assessments. Safety and tolerability will be assessed by recording of TEAEs, injection-site reactions (ISR), vital signs, 12-lead electrocardiograms (ECGs), physical examination, clinical chemistry, hematology, immunogenicity, and urinalysis.

Treatment Groups and Duration:

Subjects will be randomized in a 1:1 ratio to 240 mg LY2951742 as a manual PFS (reference) or 240 mg LY2951742 as an autoinjector (test). Each subject will receive a single dose of LY2951742 on a single occasion and have study procedures performed up to 20 weeks after study drug administration. Procedures scheduled for later than Day 2, 24 hours postdose will be performed on an outpatient basis, at the discretion of the investigator.

Number of Subjects:

Up to 160 subjects may be enrolled.

Statistical Analysis:

The $AUC(0-\infty)$; area under the concentration versus time curve from zero to time t , where t is the last time point with a measurable concentration ($AUC[0-t_{last}]$); and C_{max} will be log transformed and analyzed using an analysis of variance (ANOVA) model. The model will include fixed effects for injection device (PFS [reference] or autoinjector [test]), investigative site, and injection site. The least squares means for the PFS and autoinjector and the 90% confidence interval (CI) for the difference in means will be estimated from the ANOVA model and back transformed from the log scale to provide estimates of the geometric means and 90% CIs for the ratio of the geometric means.

Adverse events, product complaints, clinical laboratory parameters, vital signs, and ECG parameters will be assessed. They will be listed, and summarized using standard descriptive statistics.

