10.2. Populations for Analyses

10.2.1. Study Participant Disposition

A detailed description of subject disposition will be provided at the end of the study.

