10.3. Statistical Analyses

Statistical analysis of this study will be the responsibility of Eli Lilly and Company or its designee.

Pharmacokinetic and PD analyses will be conducted using subjects with evaluable PK and PD data. A subject is considered to be evaluable for PK and PD analysis if that subject is compliant with the dosing and PK and PD sampling scheme. Safety analyses will be conducted for all subjects who received at least 1 dose of study drug, whether or not they completed all protocol requirements.

Exploratory analyses of the data will be conducted as deemed appropriate. Study data may be combined with other studies for safety, PK, and/or PD analyses.

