## 8. DEFINITION OF ANALYSIS POPULATIONS

The “Safety” population will consist of all subjects who received at least 1 dose of study drug, whether or not they completed all protocol requirements.

The “Pharmacokinetic” population will consist of all subjects who are compliant with dosing and have evaluable PK data.

The “Pharmacodynamic” population will consist of all subjects who are compliant with dosing and have evaluable PD data.

All protocol deviations that occur during the study will be considered for their severity/impact and will be taken into consideration when subjects are assigned to analysis populations.

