## 9. STATISTICAL METHODOLOGY

### 9.1 General

Data listings will be provided for all data that is databased. Summary statistics and statistical analysis will only be presented for data where detailed in this SAP. For continuous data, summary statistics will include the arithmetic mean, arithmetic standard deviation (SD), median, min, max and N; for log-normal data (e.g. the PK parameters: area under the concentration versus time curve [AUC] and  $C_{max}$ ) the geometric mean and geometric coefficient of variation

(CV%) will also be presented. For categorical data, frequency count and percentages will be presented. Data listings will be provided for all subjects up to the point of withdrawal, with any subjects excluded from the relevant population highlighted. Summary statistics and statistical analyses will generally only be performed for subjects included in the relevant analysis population. For the calculation of summary statistics and statistical analysis, unrounded data will be used.

Mean change from baseline is the mean of all individual subjects' change from baseline values. Each individual change from baseline will be calculated by subtracting the individual subject's baseline value from the value at the timepoint. The individual subject's change from baseline values will be used to calculate the mean change from baseline using a SAS procedure such as Proc Univariate.

Data analysis will be performed using SAS® Version 9.3 or greater.

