## 9.3 Pharmacokinetic Assessment

### 9.3.1 Pharmacokinetic Analysis

Noncompartmental methods applied with a validated software program Phoenix WinNonlin (Pharsight Corporation, Version 6.4 or higher) to the serum concentrations of galcanezumab will be used to determine the following PK parameters, when possible:

Parameter	Units	Definition
AUC(0-∞)	day × micrograms/mL	area under the concentration versus time curve of galcanezumab from zero to infinity
%AUC(t last -∞)	Percent, %	Percent of AUC(0-∞) extrapolated of galcanezumab
AUC(0-t last )	day × micrograms/mL	area under the concentration versus time curve of galcanezumab from time zero to time t, where t is the last time point with a measurable concentration
C max	micrograms/mL	maximum observed concentration of galcanezumab
t max	day	time of maximum observed concentration of galcanezumab
t 1/2	day	half-life of galcanezumab
CL/F	L/h	apparent total body clearance of galcanezumab drug calculated after extra-vascular administration
V z /F	L	apparent volume of distribution of galcanezumab during the terminal phase after extra-vascular administration

The PK parameters of galcanezumab will be listed for individual subjects, and summary statistics will be computed by treatment (PFS, AI) and injection site location (arm, abdomen, thigh, buttocks). Additional PK parameters may be calculated, as appropriate. The software and

version used for the final analyses will be specified in the CSR. Any exceptions or special handling of data will be clearly documented within the final study report.

Formatting of tables, figures and abbreviations will follow the Eli Lilly Global PK/PD/TS Tool: NON-COMPARTMENTAL PHARMACOKINETIC STYLE GUIDE. The version of the tool effective at the time of PK analysis will be followed.

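### Could the PK population rule let under-delivery by a device drop out of the autoinjector–syringe comparison?

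*SAP*

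**What the plan says.** SAP Section 8 states that the PK population "will consist of all subjects who are compliant with dosing and have evaluable PK data". It adds that protocol deviations will be weighed for severity and impact and "will be taken into consideration when subjects are assigned to analysis populations". Protocol Section 10.3 has a similar rule: a subject is evaluable "if that subject is compliant with the dosing and PK and PD sampling scheme". Protocol Appendix 1 defines compliance in general terms, as adherence to trial, GCP and regulatory requirements. It does not mention a device that malfunctions.

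SAP Section 9.3.2 gives one ANOVA for Cmax and the AUCs, with device, investigative site and injection site as fixed effects. SAP Section 9.1 sets where it is run: "Summary statistics and statistical analyses will generally only be performed for subjects included in the relevant analysis population".

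Several outputs bear on excluded subjects and device problems:

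- Listings cover all subjects up to withdrawal, "with any subjects excluded from the relevant population highlighted" (SAP Section 9.1).
- The protocol synopsis says of complaints and safety data: "Adverse events, product complaints, clinical laboratory parameters, vital signs, and ECG parameters will be assessed. They will be listed, and summarized". Protocol Section 9.2.2 has sites report complaints within 24 hours, and Section 10.3.1.1 has product- and device-related complaints counted.
- On disposition, Protocol Section 10.2.1 says: "A detailed description of subject disposition will be provided at the end of the study".
- On PK data, SAP Section 9.3.1 says: "Any exceptions or special handling of data will be clearly documented within the final study report".

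SAP Section 3 allows additional analyses, to be identified in the study report, and refers to a separate document of table, figure and listing shells for the detailed outputs.

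**The concern.** The syringe, plunger and needle are the same in both presentations (Protocol Section 3.2), so what differs is how the dose is delivered. The study is the bridge from the Phase 3 syringe to the planned commercial autoinjector (Protocol Section 3.1). If an autoinjector under-delivers, that could be regarded as part of what the comparison should capture.

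The population wording leaves the matter open. A subject whose device was used correctly but gave only part of the dose can be read as compliant, because the procedure was followed, or as not compliant, because 240 mg was not received. The study is open-label, deviations are weighed case by case, and no date is given for fixing the populations.

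If such failures were more common with the autoinjector and the true ratio with full delivery were below 1, leaving those subjects out would move the reported ratio toward 1. Neither document plans the ratio and 90% CI with and without the excluded subjects.

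**Working it through.** **Inputs.** From Protocol Section 10.1 and SAP Section 7: 80 per arm, CV about 35%, true ratio 0.95, 12.5% not contributing, limits 0.8 to 1.25, 90% CI, power about 90%. From Protocol Section 7.1.1: two devices of 120 mg per dose, so one device lost is half the dose. From Protocol Section 3.2: exposure is roughly dose proportional, so delivered fraction f is taken as exposure fraction. The documents give no failure count k and no f; both are assumptions.

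**The plan's own figure.** Evaluable subjects per arm: 80 × (1 − 0.125) = 70. Log-scale SD: √ln(1 + 0.35²) = 0.340. Exact two-one-sided-tests power at ratio 0.95 is 0.9075, so the stated 90% is reproduced. The 90% CI half-width is t(0.95, 138 df) × 0.340 × √(2/70) = 0.0952 on the log scale. This gives an expected interval of 0.864 to 1.045 around 0.95. An observed ratio below 0.8 × e^0.0952 = 0.880 would miss the lower limit.

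**Failures in the autoinjector arm only.** If k of 70 subjects receive fraction f, the all-dosed ratio is R × f^(k/70). For k = 4 and f = 0.5: 0.95 × 0.5^(4/70) = 0.95 × 0.961 = 0.913. The table gives the simulated chance that the 90% CI lies within 0.8–1.25 at R = 0.95 (200,000 trials per scenario; pooled two-sample t interval; site and injection-site effects omitted). The all-dosed ratio is in brackets.

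| k | Kept, f = 0.5 | Kept, f = 0.75 | Kept, f = 0.9 | Dropped |
|---|---|---|---|---|
| 2 | 83% (0.931) | 88% (0.942) | 90% (0.947) | 90% |
| 4 | 71% (0.913) | 85% (0.935) | 89% (0.944) | 90% |
| 7 | 49% (0.886) | 79% (0.923) | 87% (0.940) | 89% |

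One half-dose failure gives 87% kept against 91% dropped. With no failures it is 91% either way.

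**Sensitivity.**

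- Ratio 1.00, k = 4: 92%, 97% and 97% kept at f = 0.5, 0.75 and 0.9, against about 97% dropped.
- Ratio 1.10, k = 4: 88%, 80% and 75% kept, against about 70% dropped. The direction reverses.
- Four failures in each arm at 0.95: 87%, 90% and 91% kept, against 89% dropped.
- The 12.5% allowance may already cover excluded subjects. Starting from 70 + k autoinjector subjects and ending at 70 after exclusion (ratio 0.95, f = 0.5) gives 73% against 91% for k = 4 and 55% against 91% for k = 7. The picture is slightly milder and otherwise the same.

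**Reading the texts together.** The Appendix 1 definition concerns adherence. A subject correctly given the assigned device has arguably adhered even if the device then faltered, so keeping that subject is the more natural reading. The stated objective, however, is the relative bioavailability of 240 mg, so a reader could also defend leaving out someone who did not receive 240 mg. The wording permits either and pushes toward neither. The outlier procedure is not a back door: SAP Section 9.3.1.5 bars its use to remove complete profiles.

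**The case for a change.** The strongest case for changing the plan starts from the fact that device failure is foreseen. Protocol Section 7.1 has sites return autoinjectors that do not operate correctly, with a complaint form, yet the SAP has no rule for the subjects concerned. The reporting that exists shows who was left out or what failed, not what this did to the ratio. With-and-without results in SAP Section 9.3.1.5 cover only a suspect value within a profile, or fewer than six values. A supportive analysis chosen under SAP Section 3 would be chosen after the data are seen. In a re-run with four half-dose autoinjector failures at 0.95, 19% of simulated trials met 0.8–1.25 with those subjects dropped and missed it with them kept. The remedy would be cheap: one extra run of the ANOVA, one table and a date.

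Part of this stands. The protocol and SAP pre-specify no with-and-without ratio and state no date for fixing assignment. The rest is conditional. The harm needs failures to occur, to be large or frequent, to fall mainly in one arm, and then to be excluded. Doses are given on site by authorized staff with the same syringe in both arms, which makes a large imbalance less likely. The analysis sections also set no pass rule; 0.8–1.25 appears only in the sample-size text. The extra output would leave the primary analysis and every stated figure unchanged.

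**Conclusion.** No change to the plan is needed. The wording leaves a detail unwritten that analysts can settle sensibly: how a device malfunction is classed when populations are assigned. If a dosed subject with usable PK data is left out, the exclusion should be visible in the planned listings, complaint counts and documented handling. An additional run of the same ANOVA is already allowed.

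The size rests wholly on assumed failures. It is nil with none, about 4 points with one half-dose failure (91% against 87%), and at most about 2 points at ratio 0.95 when 90% of the dose is delivered. It becomes large only with several half-dose failures confined to one arm: 4 of 70 is 5.7% of that arm and 7 of 70 is 10%. The direction depends on the true ratio.

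The conclusion assumes 70 evaluable per arm, CV 35% and exposure proportional to delivered dose. It is drawn from the protocol and SAP alone, since the output shells were not available. A note on classification and timing would be harmless, but a sound primary result does not depend on it.

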## 9. STATISTICAL METHODOLOGY

### 9.1 General

Data listings will be provided for all data that is databased. Summary statistics and statistical analysis will only be presented for data where detailed in this SAP. For continuous data, summary statistics will include the arithmetic mean, arithmetic standard deviation (SD), median, min, max and N; for log-normal data (e.g. the PK parameters: area under the concentration versus time curve [AUC] and  $C_{max}$ ) the geometric mean and geometric coefficient of variation

(CV%) will also be presented. For categorical data, frequency count and percentages will be presented. Data listings will be provided for all subjects up to the point of withdrawal, with any subjects excluded from the relevant population highlighted. Summary statistics and statistical analyses will generally only be performed for subjects included in the relevant analysis population. For the calculation of summary statistics and statistical analysis, unrounded data will be used.

Mean change from baseline is the mean of all individual subjects' change from baseline values. Each individual change from baseline will be calculated by subtracting the individual subject's baseline value from the value at the timepoint. The individual subject's change from baseline values will be used to calculate the mean change from baseline using a SAS procedure such as Proc Univariate.

Data analysis will be performed using SAS® Version 9.3 or greater.

## 9.2 Demographics and Subject Disposition

Subject disposition will be listed. The demographic variables age, sex, race, ethnicity, site ID, body weight, height, body mass index and smoking status will be summarized and listed. All other demographic variables will be listed.

## 9.3 Pharmacokinetic Assessment

### 9.3.1 Pharmacokinetic Analysis

Noncompartmental methods applied with a validated software program Phoenix WinNonlin (Pharsight Corporation, Version 6.4 or higher) to the serum concentrations of galcanezumab will be used to determine the following PK parameters, when possible:

Parameter	Units	Definition
AUC(0-∞)	day × micrograms/mL	area under the concentration versus time curve of galcanezumab from zero to infinity
%AUC(t last -∞)	Percent, %	Percent of AUC(0-∞) extrapolated of galcanezumab
AUC(0-t last )	day × micrograms/mL	area under the concentration versus time curve of galcanezumab from time zero to time t, where t is the last time point with a measurable concentration
C max	micrograms/mL	maximum observed concentration of galcanezumab
t max	day	time of maximum observed concentration of galcanezumab
t 1/2	day	half-life of galcanezumab
CL/F	L/h	apparent total body clearance of galcanezumab drug calculated after extra-vascular administration
V z /F	L	apparent volume of distribution of galcanezumab during the terminal phase after extra-vascular administration

The PK parameters of galcanezumab will be listed for individual subjects, and summary statistics will be computed by treatment (PFS, AI) and injection site location (arm, abdomen, thigh, buttocks). Additional PK parameters may be calculated, as appropriate. The software and

version used for the final analyses will be specified in the CSR. Any exceptions or special handling of data will be clearly documented within the final study report.

Formatting of tables, figures and abbreviations will follow the Eli Lilly Global PK/PD/TS Tool: NON-COMPARTMENTAL PHARMACOKINETIC STYLE GUIDE. The version of the tool effective at the time of PK analysis will be followed.

### 9.3.1.1 General PK Parameter Rules

- Actual sampling times will be used in the final analyses of individual PK parameters, except for non-bolus pre-dose sampling times which will be set to zero. For non-bolus, multiple dose profiles, the pre-dose time will be set to zero unless a time deviation falls outside of the protocol blood collection time window which is considered to impact PK parameter derivation.
- $C_{max}$  and  $t_{max}$  will be reported from observed values. If  $C_{max}$  occurs at more than one time point,  $t_{max}$  will be assigned to the first occurrence of  $C_{max}$ .
- AUC parameters will be calculated using a combination of the linear and logarithmic trapezoidal methods (linear-log trapezoidal rule). The linear trapezoidal method will be applied up to  $t_{max}$  and then the logarithmic trapezoidal method will be used after  $t_{max}$ . The minimum requirement for the calculation of AUC will be the inclusion of at least three consecutive serum/plasma concentrations above the lower limit of quantification (LLOQ), with at least one of these concentrations following  $C_{max}$ . AUC(0- $\infty$ ) values where the percentage of the total area extrapolated is more than 20% will be flagged. Any AUC(0- $\infty$ ) value excluded from summary statistics will be noted in the footnote of the summary table.
- Half-life ( $t_{1/2}$ ) will be calculated, when appropriate, based on the apparent terminal log-linear portion of the concentration-time curve. The start of the terminal elimination phase for each subject will be defined by visual inspection and generally will be the first point at which there is no systematic deviation from the log-linear decline in serum/plasma concentrations. Half-life will only be calculated when a reliable estimate for this parameter can be obtained comprising of at least 3 data points. If  $t_{1/2}$  is estimated over a time window of less than 2 half-lives, the values will be flagged in the data listings. Any  $t_{1/2}$  value excluded from summary statistics will be documented in the footnote of the summary table.
- A uniform weighting scheme will be used in the regression analysis of the terminal log-linear portion of the concentration-time curve.
- The parameters based on observed  $C_{last}$  will be reported.

### 9.3.1.2 Individual PK Parameter Rules

- Only quantifiable concentrations will be used to calculate PK Parameters with the exception of special handling of certain concentrations reported below the lower limit of

---

quantitation (BQL). Serum/plasma concentrations reported as BQL will be set to a value of zero when all of the following conditions are met:

- The compound is non-endogenous.
  - The samples are from the initial dose period for a subject or from a subsequent dose period following a suitable wash-out period.
  - The time points occur before the first quantifiable concentration.
- All other BQL concentrations that do not meet the above criteria will be set to missing.
  - Also, where two or more consecutive concentrations are BQL towards the end of a profile, the profile will be deemed to have terminated and therefore any further quantifiable concentrations will be set to missing for the calculation of the PK parameter s unless it is considered to be a true characteristic of the profile of the drug.

#### 9.3.1.3 Individual Concentration vs. Time Profiles

- Individual concentrations will be plotted utilizing actual sampling times.
- The terminal point selections will be indicated on a semi-logarithmic plot.

#### 9.3.1.4 Average Concentration vs. Time Profiles

- The average concentration profiles will be graphed using scheduled (nominal) sampling times.
- The average concentration profiles will be graphed using arithmetic average concentrations.
- The pre-dose average concentration for single-dose data from non-endogenous compounds will be set to zero. Otherwise, only quantifiable concentrations will be used to calculate average concentrations.
- Concentrations at a sampling time exceeding the sampling time window specified in the protocol, or  $\pm 10\%$ , will be excluded from the average concentration profiles.
- Concentrations excluded from the mean calculation will be documented in the final study report.
- A concentration average will be plotted for a given sampling time only if  $2/3$  of the individual data at the time point have quantifiable measurements that are  $\pm 10\%$ . An average concentration estimated with less than  $2/3$  but more than 3 data points may be displayed on the mean concentration plot if determined to be appropriate and will be documented within the final study report.

### 9.3.1.5 Treatment of Outliers during Pharmacokinetic Analysis

Application of this procedure to all PK analyses is not a requirement. Rather, this procedure provides justification for exclusion of data when scientifically appropriate. This procedure describes the methodology for identifying an individual value as an outlier for potential exclusion, but does not require that the value be excluded from analysis. The following methodology will not be used to exclude complete profiles from analysis.

